	
from Baseline to Month 6 and to Month 12.
 
Secondary Endpoints:
 
 
• ARR (after 12 months of Rebif treatment)
 
• Adherence (after 6 and 12 months of Rebif treatment)
 
• MusiQoL (compare Baseline with after 6 and 12 months of Rebif treatment)
 
• Reason/s for discontinuation of initial MS treatment (oral or injectable).
 
 
Additional Secondary Endpoints:
 
 
• Correlation between TSQM v II and ARR; TSQM v II and adherence; TSQM v II and reason for discontinuation
 
• Correlation between MusiQoL and ARR; MusiQoL and adherence; MusiQoL and reason for discontinuation
 
• Correlation between TSQM v II subscales and adherence
 
• Correlation between TSQM v II subscales and reasons for discontinuation
 
• Difference between TSQM v II subscales at Baseline and after 6 and 12 months of Rebif treatment
 
• ARR before study entry compared to ARR at study end
 
• Association between ARR and treatment adherence.
 

Study Design
	
This is a prospective, multicenter, open label, uncontrolled, non-interventional, single arm study to measure treatment satisfaction of RRMS patients on Rebif after discontinuing initial first-line treatment.
 
This study consists of three visits:
 
 
• Visit 1: Baseline
 

	
 
• Visit 2: Month 6
 
• Visit 3: Month 12
 
 
This study will enroll RRMS patients who have discontinued their oral or injectable first-line MS medication and have decided to initiate subcutaneous Interferon beta-1a (IFN <math>\beta</math> -1a) (Rebif) treatment before Baseline measurements. MusiQoL and TSQM v II will be measured at Baseline, Month 6 and Month 12. Relapses and adherence will be assessed at Month 6 and Month 12. Adherence to Rebif therapy will be collected electronically using RebiSmart 2.0.
 
Since this is a non-interventional study, there will not be any study required clinical interventions and laboratory assessments.

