
Study Population and Eligibility Criteria
	
RRMS patients who have discontinued their initial MS treatment and for whom MS treatment is required according to the decision of the HCP and patient.
 
Inclusion Criteria:
 
The patient can be included when the patient
 
 
• Is male or female, 18 to 65 years of age (both inclusive), at the time of informed consent
 
• Is diagnosed with RRMS according to McDonald criteria 2010
 
• Has discontinued treatment with dimethyl fumarate (Tecfidera), teriflunomide (Aubagio), glatiramer acetate (Copaxone®), intramuscular IFN<math>\beta</math>-1a (Avonex®), pegylated interferon (Plegridy®), subcutaneous IFN<math>\beta</math>-1b (Betaferon®) or fingolimod (Gilenya®) within 6 months prior to Visit 1
 

- Is currently treated with Rebif using RebiSmart 2.0, for a maximum of 6 months prior to Visit 1
- Has a score on the Expanded Disability Status Scale (EDSS) between 0 to 5.0 inclusive
- Is willing and able to give informed consent.

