Data Analysis	
Statistical analysis will be mainly descriptive. Descriptive statistics (n, mean, standard deviation, median, first quartile [Q1], third quartile [Q3], minimum, maximum) will be provided for continuous variables. Frequencies and percentages will be presented for categorical and ordinal variables. Where appropriate, 95% confidence intervals (CIs) will be presented.
 
All analyses will be performed on subjects who received at least one dose of Rebif following enrolment in the study.
 
Primary Endpoint analysis:
 
A paired two-sided t-test of the global satisfaction score (TSQM score) will be used to test the null hypothesis that there is no difference in the global satisfaction score (TSQM score) between 6, 12 months and Baseline. The corresponding 95% two-sided CI will be presented.

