### Schedule of Assessments

Activity	Visit 1 Baseline	Visit 2 Month 6	Visit 3 Month 12 (End of Study Visit)
Patient Informed Consent	X		
Inclusion/Exclusion Criteria	X		
Demographic information	X		
Medical History / Concomitant diseases / Prior MS medications	X		
Multiple Sclerosis History (including relapses within 2 years before study entry)	X		
MS medication related adverse events and associated concomitant medications	X		
Vital Signs	X	X	X
Physical Examination	X	X	X
Neurological Examination	X	X	X
Relapse Assessment		X	X
TSQM Version II evaluation	X	X	X
MusiQoL evaluation	X	X	X
Document reasons for discontinuation of previous MS therapy	X		
Therapy with Rebif	X	X	X
Evaluation of Adherence to Therapy		X	X
Safety Recording and Reporting		X	X

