## 16.2 Secondary Endpoint Analyses

### Annualized Relapse Rate (ARR):

The quantitative variables,

- Annualized Relapse Rate before study entry
- Number of relapses during the study
- Annualized Relapse Rate on study

will be summarized for prior MS Therapy categories and overall using descriptive statistics from Safety Analysis Set.

Annualized Relapse Rate before study entry = (No. of Relapses within 24 months prior to written informed consent / (30.4375\*24)) \* 365.25

Annualized Relapse Rate on study = (Sum of No. of Relapses at month 6 and month 12/ Time on Study) \* 365.25

where,

Time on Study (days) = (Date of Study Completion or Date of study discontinuation - Date of first Rebif administration +1)

95% Confidence Interval (CI) will also be provided for Annualized Relapse Rate before study entry and on study.

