#### **Adherence Evaluation:**

Adherence (%) will be calculated for each subject as 100 x the number of injections the subject administered divided by the expected number of injections over 6 or 12 Months. If the subject terminates earlier than 12 months, the expected number of completed injections will be based on the subject's time on study.

The quantitative variable

- Adherence (%)

will be summarized for month 6 and month 12/End of treatment using descriptive statistics from Safety Analysis Set.

Adherence (%) = (No. of injections the subject administered / Expected No. of injections over 6 or 12 Months) x 100.

Number of injections the subject administered = Expected number of injections over 6 or 12 Months - Total No. of estimated missed injections since baseline visit.

The expected number of injections 3 times weekly (i.e. 3\*24 weeks (6 months) = 72 expected injections over 6 months and 144 expected number injections over 12 months).

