### **16.3 Other Endpoint Analyses**

#### **Relapse Assessment:**

The qualitative variables

- Subject experienced any MS relapses since last visit (Yes / No)

will be summarized for month 6, month 12 using descriptive statistics from Safety Analysis Set.

The quantitative variable

- No. of Relapses since last visit

will be summarized for month 6, month 12 as number and percentage from Safety Analysis Set.

Listing will be provided for Relapse assessment.

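### On-study ARR counts relapses from Visit 1 but counts time from the first Rebif dose, up to 6 months earlier, so a completer's rate can come out up to 33% too low

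*SAP*

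**What the plan says.** Section 16.2 (Annualized Relapse Rate) builds the on-study rate from "Sum of No. of Relapses at month 6 and month 12/ Time on Study", scaled by 365.25. It then sets "Time on Study (days) = (Date of Study Completion or Date of study discontinuation - Date of first Rebif administration +1". This is the only definition of Time on Study in the SAP.

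Four other places determine what the numerator and denominator cover:

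- **Relapse counting.** Section 16.3 (Relapse Assessment) gives the quantity collected at Months 6 and 12 as "No. of Relapses since last visit". In the Section 6 Schedule of Assessments, relapse assessment is marked only at Months 6 and 12. Baseline has "Multiple Sclerosis History (including relapses within 2 years before study entry" as history.
- **Eligibility.** Section 6 requires that the patient "Is currently treated with Rebif using RebiSmart 2.0, for a maximum of 6 months prior to Visit 1".
- **Comparator period.** The rate before study entry uses relapses in the 24 months before written informed consent, divided by 30.4375 × 24 days. Consent is taken at Visit 1.
- **Purpose.** Section 6 lists "ARR before study entry compared to ARR at study end" among the additional secondary endpoints, and change in ARR on switching to Rebif is a secondary objective.

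Time on study appears twice more in Section 16.2: as the basis for expected injections in patients who leave early, and, in log form, as an independent variable in the relapse regression.

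**The concern.** The numerator and denominator of a rate must cover the same interval. Here the relapse count opens at Visit 1, while the clock opens at the first Rebif administration, which the eligibility criteria place up to 6 months earlier. Those lead-in months are event-free by construction in the on-study rate. They also belong to the 24 months before consent, so any relapse in them is counted in the before-entry rate. The months are in both denominators, but their relapses are in only one numerator.

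The error runs in one direction: it lowers the on-study rate and so favours the switch to Rebif. The study has a single arm, so no comparator would reveal the artefact, and a larger sample would not reduce it.

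**Working it through.** **Plan's own figure.** The SAP states no expected ARR, so there is none to reproduce. Its before-entry denominator is internally consistent: 30.4375 × 24 = 730.5 days.

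**Inputs.**
- F = months from Visit 1 to end of study; 12 for a completer (Section 6, Exposure).
- u = months on Rebif before Visit 1; 0 to 6 (Section 6, inclusion criteria). The SAP gives no distribution for u.

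**Step 1: effect on a completer's rate.** For one patient with a fixed number of relapses, the count cancels:

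rate as written / rate from Visit 1 = F/(F+u) = 12/(12+u)

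No assumption about the relapse rate is needed.

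| u (months) | 12/(12+u) | too low by |
|---|---|---|
| 0 | 1.000 | 0% |
| 1 | 0.923 | 7.7% |
| 2 | 0.857 | 14.3% |
| 3 | 0.800 | 20.0% |
| 4 | 0.750 | 25.0% |
| 5 | 0.706 | 29.4% |
| 6 | 0.667 | 33.3% |

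A true rate of 0.30 would be reported as 0.30 × 0.80 = 0.24 at u=3 and 0.30 × 0.667 = 0.20 at u=6. Working in days with the SAP's +1 gives the same picture: a completer with one relapse has an ARR of 0.997 from Visit 1, against 0.798 (u=3) and 0.666 (u=6) as written.

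**Step 2: early leavers.** The ratio F/(F+u) worsens as F shrinks. With u=6, and including the +1 day, the rate is 49.9% too low at F=6 and 66.4% too low at F=3.

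**Step 3: average, under an assumption.** If u were uniform on 0 to 6 months, the mean factor for completers would be (1/6)∫12/(12+u)du = 2·ln(1.5) = 0.811, about 19% too low.

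**Step 4: the before/after comparison.** With a constant true rate, the on-study/before ratio should be 1.00. As written it is 0.80 at u=3 and 0.667 at u=6. Starting the clock at Visit 1 restores 1.00.

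As an illustration, suppose Rebif halves the rate and u=6:
- Before-entry rate, relative to the untreated rate: (18×1 + 6×0.5)/24 = 0.875
- Ratio as written: 0.5×(12/18)/0.875 = 0.381
- Ratio with a Visit 1 clock: 0.5/0.875 = 0.571
- Ratio with a Visit 1 clock and the before window ended at Rebif start: 0.500

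The Visit 1 clock therefore removes the artefact in the on-study rate but leaves on-Rebif months in the before-entry rate.

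**Step 5: adherence, only if the same definition is carried over.** Missed injections are the "Total No. of estimated missed injections since baseline visit". Assume a patient who leaves 12 weeks after Visit 1 with 9 missed injections and a 12-week lead-in. At 3 injections a week, a Visit 1 clock gives (36−9)/36 = 75.0%, and the first-dose clock gives (72−9)/72 = 87.5%.

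**Regression.** Log time enters as a covariate, not an offset, so no size is claimed there.

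**The case against.** The strongest reply is that the first Rebif administration means the first one on study. Section 6 (Data Analysis) restricts analyses to patients with "at least one dose of Rebif following enrolment in the study". Section 15 has a separate label for the start of Rebif therapy when it computes treatment duration, and Section 16.2 does not use it. The variable is also named Time on Study. On that reading the mismatch is a matter of days.

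This is a plausible account of intent, but it does not settle the text. The Data Analysis sentence says who is analysed, not when time starts. The operative analysis-set definition in Section 10 does not carry the post-enrolment condition, and neither does the ARR formula. A programmer following Section 16.2 literally would take the first-ever Rebif date. What stands is that the bias is conditional on the literal reading.

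Other objections have some force:

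- **Adherence.** That paragraph uses time on study in ordinary prose and counts missed injections from baseline. Importing the first-dose clock would give a patient with a 6-month lead-in who leaves at month 9 an expected 15 × 12 = 180 injections, more than the 144 set for a completer. The authors may well have had a baseline clock in mind, so the 75.0% versus 87.5% example is conditional.
- **Average bias.** The prior drug must have been stopped within 6 months before Visit 1, and a gap between therapies shortens the lead-in. The 19% is illustrative; only the range rests on the SAP.
- **Consequence.** ARR is secondary, Section 16.2 plans summaries and confidence intervals without a before/after test, and Section 11 calls all tests explorative.

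**Conclusion.** The definition is wrong as written. On its literal reading, a 12-month completer's on-study ARR is 0% to 33% too low, depending on 0 to 6 months of lead-in, and early leavers are affected more. The range follows from the eligibility criterion and the formula alone. The average is unknown because the SAP gives no lead-in distribution. With no true change in relapse rate, the listed before/after comparison would show a fall of the same size in completers.

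If the first dose after enrolment was intended, the rate is essentially unaffected, but the SAP then leaves a start date that can be read up to 6 months apart. It should be fixed before analysis. It is not critical: the endpoint is secondary and descriptive, and the primary TSQM analysis does not use this variable.

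**What to change.** Define Time on Study in Section 16.2 as the date of study completion or discontinuation minus the date of Visit 1 (informed consent), plus 1. State that the same variable is used for early leavers' expected injections and in the relapse regression. If the first dose after enrolment was intended, say so explicitly.

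Two additions would help, but the correction does not depend on them:

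- Report a pooled ARR (total relapses divided by total person-years) with a count-based 95% CI, because subject-level rates are unstable with short follow-up.
- As a sensitivity analysis, end the before-entry window at the Rebif start date, since the main fix leaves on-Rebif months in that period.

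The cost is a wording change and minor programming; the dates are already used elsewhere in the SAP. Compared with the literal definition, the on-study ARR will look less favourable; compared with a first-dose-after-enrolment reading it will hardly change. The sensitivity analysis needs dated relapses before consent, which may not be available for every patient.

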## 7. Sample Size

A sample size of 106 subjects will be required to have 85% power to detect at least an 8 point difference in mean TSQM scores between Baseline and Month 6 or Month 12 measurements, with the standard deviation (SD) of 27.5 and a two sided significance level of 5%. Assuming a 20% drop out rate, approximately 133 patients will be enrolled into the study in the Netherlands, Switzerland and Belgium.

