## **12. Trial Subjects**

### **12.1 Disposition of Subjects and Discontinuations**

A table with

- Number of subjects screened
- Number of screen failure subjects
- Number of subjects enrolled in the study
- Number of subjects in Safety Analysis Set
- Number of Safety Analysis Set subjects who completed the study.
- Number of Safety Analysis Set subjects who discontinued the study together with primary reason for discontinuation (Lost to follow-up, Adverse event/ Serious adverse event, Discontinuation of Rebif is desired or considered necessary by the Investigator and/or the subject, Occurrence of an exclusion criterion, Subject withdraws consent (Reasons for Withdraws consent), Discontinuation of Rebif for any other reason (Reason for discontinuation)).

will be presented. Percentages will be calculated.

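### The on-study ARR divides relapses counted at Months 6 and 12 by time running to the discontinuation date, so unassessed time of early leavers can lower the rate

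*SAP*

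**What the plan says.** SAP Section 16.2 (Annualized Relapse Rate) annualizes "Sum of No. of Relapses at month 6 and month 12/ Time on Study", where "Time on Study (days) = (Date of Study Completion or Date of study discontinuation - Date of first Rebif administration +1".

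The relapse counts come from two visits only. Section 6 states: "Relapses and adherence will be assessed at Month 6 and Month 12". Section 16.3 describes the recorded variable as "No. of Relapses since last visit", so the Month 6 count starts at Visit 1 and the Month 12 count starts at Visit 2. The Schedule of Assessments puts the relapse assessment at Visits 2 and 3 and heads the last column "Visit 3 Month 12 (End of Study Visit").

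Early leavers are expected. Section 7 says: "Assuming a 20% drop out rate, approximately 133 patients will be enrolled". Section 12.1 tabulates the "primary reason for discontinuation (Lost to follow-up, Adverse event/ Serious adverse event" and other reasons.

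The general rule on missing data in Section 11 is that absent values are not imputed unless the SAP specifies otherwise. Section 16.2 gives no special rule for a missing relapse count.

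**The concern.** A rate needs a count and a time at risk that cover the same interval. Here the count stops at the last relapse assessment, while the clock runs to the discontinuation date. For a patient lost after Month 6 with no closing assessment, the months in between enter as if observed and relapse-free. For a patient lost before Month 6 there is no on-study count at all, yet Time on Study is positive.

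At this end of the window the error has one direction: it lowers the on-Rebif rate. The pre-study rate divides relapses over 24 months by 24 months, so its count and its time match. Section 6 lists a comparison of the pre-study and on-study ARR among the additional secondary endpoints, and a diluted on-study rate would flatter Rebif in it. The SAP also leaves the handling of an incomplete sum open, so one formula can give different results and different patient sets depending on how it is programmed.

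**Working it through.** **The plan's own figure.** The SAP gives no expected ARR or relapse count to reproduce. The only design figure used here is dropout: 106 / (1 − 0.20) = 132.5, rounded up to 133, which agrees with Section 7. That allows for 133 − 106 = 27 leavers.

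**One patient, both intervals counted from Visit 1.**
- Last assessed at Month 6, discontinuation dated Month 9: 6 assessed months over 9, ratio 6/9 = 0.67, so the rate is 33% low.
- One relapse by Month 6, discontinuation dated Month 11: the SAP formula gives 12/11 = 1.09 per year. Over the six assessed months the rate is 12/6 = 2.00.

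**Trial level.** Assumptions, none of which the SAP states:
- a constant relapse rate, the same in leavers and completers;
- visits exactly at Months 6 and 12;
- 20% dropout, uniform over 0 to 12 months;
- no closing relapse assessment, and a discontinuation date equal to the true exit date;
- no Rebif before Visit 1, to isolate the end-date effect.

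The expected ratio of the SAP-formula ARR to the true ARR is assessed months / Time on Study. Completers (80%) have ratio 1. Leavers before Month 6 (10%) have no count. Leavers from Month 6 on (10%) have ratio 6/t, which averages ln 2 = 0.693 for t uniform on 6 to 12.

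(a) Absent counts taken as zero:
- mean of patient ARRs: 0.80 + 0.10 × 0 + 0.10 × 0.693 = 0.869, about 13% low;
- pooled: (0.8 × 12 + 0.1 × 6) / (0.8 × 12 + 0.2 × 6) = 10.2 / 10.8 = 0.944, about 6% low.

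(b) Patients with no count left missing, and the Month 6 count used alone for later leavers:
- mean: (0.80 + 0.10 × 0.693) / 0.90 = 0.966;
- pooled: 10.2 / (9.6 + 0.1 × 9) = 10.2 / 10.5 = 0.971;
- so about 3% low either way.

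(c) Any patient without a Month 12 count left missing: ratio 1.00. There is no dilution, but all leavers drop out of the ARR.

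(d) Relapses assessed at exit: ratio 1.00.

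For dropout of 10% to 30%, (a) runs from 0.94 to 0.80 (mean) and 0.97 to 0.91 (pooled). Case (b) runs from 0.98 to 0.95 (mean) and 0.99 to 0.95 (pooled).

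**The start of the same window.** Time on Study begins at the first Rebif dose, which the inclusion criteria allow up to 6 months before Visit 1. The on-study relapse count begins at Visit 1. A completer with 3 months of prior Rebif therefore has ratio 12/15 = 0.80, and with 6 months 12/18 = 0.67. Moving only the end date would leave this in place: the patient last assessed at Month 6, with 3 months of prior Rebif, would still have 6 counted months over 9.

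**The case against.** The dilution needs three things that the SAP does not state: no relapse assessment at early exit, a discontinuation date later than the last assessment, and a patient kept in the ARR with the absent count taken as zero or ignored. If any one fails, there is no effect. The document also leans towards a closing assessment for some leavers. Visit 3 is labelled as the end-of-study visit, and Section 16.2 summarises adherence at Month 12 or end of treatment. Exit procedures are ordinarily set out in the protocol and case report form, which are not at hand. This stands. A reader might infer that the on-Rebif ARR is certainly biased downward; the SAP supports only that it can be, and in that direction. What the objection does not remove is the patient lost to follow-up, who is the least likely to have a closing visit and for whom the stated formula still runs the clock to the discontinuation date.

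A reader might also infer that every patient lost before Month 6 is given an ARR of 0. Section 11 points the other way, because setting an absent count to zero is an imputation and Section 16.2 specifies none. Case (b) is the reading closest to that rule, so 13% is an upper scenario and not the expected effect.

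Nor do these percentages carry over to the relapse regression in Section 16.2. Log time on study is a candidate covariate there, screened at p ≤ 0.15 with an estimated coefficient. It is not a fixed offset, and no effect on that model has been calculated.

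Finally, ARR is a secondary endpoint. Section 16.2 plans summaries with confidence intervals and no before/after test, and Section 11 makes all tests exploratory. That limits the weight of the point.

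**Conclusion.** The point holds in conditional form. The stated numerator and denominator need not end on the same day. Where they differ at the end of follow-up, unassessed time is added and the on-Rebif ARR can only fall.

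Under the assumptions above, at 20% dropout, the mean ARR is about 3% low on the reading closest to Section 11. It is about 13% low (6% pooled) if absent counts become zeros, and 0% low if leavers are assessed at exit or their incomplete sums are left missing. These figures assume that leavers and completers relapse at the same rate. If they do not, dropping leavers shifts the ARR in a way this calculation does not measure.

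This is a minor-to-moderate point on an exploratory secondary endpoint. It is worth correcting because the derivation currently leaves both the result and the set of patients analysed to the programmer.

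**What to change.** In Section 16.2, define the ARR time at risk as the interval over which relapses were actually assessed. It would start at Visit 1, where the first count begins, and end at the last completed relapse assessment: Month 6, Month 12 or an early end-of-study visit. Under the assumptions above this brings the ratio to 1.00.

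State that on-study ARR is missing, not zero, for a patient with no post-baseline relapse assessment, and report how many such patients there are. State that where only the Month 6 count exists, it is divided by the time to that assessment. Use the same time variable in the relapse regression for consistency. Keep the discontinuation date for the disposition table.

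The cost is a few lines of SAP text and the use of visit dates. There is slightly less person-time, and patients with no assessment drop out of the ARR. With uniform 20% dropout and no closing visits, that would be about half of the 27 leavers.
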